1. INTRODUCTION

Background

A novel coronavirus, now termed Severe Acute Respiratory Syndrome Coronavirus 2 (SARS-CoV-2), arose late in 2019.² The first confirmed cases occurred in December in Wuhan, Hubei province, China. It now infects people on six continents,

spreading person to person. The World Health Organization (WHO) classified it as a global pandemic on March 11, 2020. As of April 6, 2020, there are more than 1.2 million confirmed cases and more than 70,000 deaths attributed to this virus. Every person on Earth, as well as every United States Veteran, is at risk. This is the emergent public health threat of our time.

SARS-CoV-2 is a single stranded RNA virus³ related to severe acute respiratory syndrome-related coronavirus (SARS-CoV-1).⁴ SARS-CoV-2 is thought to be transmissible largely by respiratory droplets or direct contact,⁵ but might also be transmitted through aerosolization.⁶ SARS-CoV-2 disease severity ranges from no to minimal symptoms, mildly symptomatic with cough and dyspnea, to severe respiratory distress with multi-organ failure requiring admission to an intensive care unit and emergent ventilator support.⁷ Although data are evolving, the severity of illness varies with age, co-existing comorbidities, and biological sex, with older age, people with pre-existing cardiovascular disease, and males manifesting greater disease severity.⁸

A worldwide effort is in place to contain and suppress human-to-human transmission.⁹ These public-health strategies aim to slow the rate of spread and reduce the burden on critical care infrastructure. However, we also need effective therapeutics. Vaccine trials are underway but potential approvals are at least a year away.¹⁰ Development of new drugs de novo to treat SARS-CoV-2 will likely take even longer. Thus, the most expedient therapeutic strategy to confront this pandemic will repurpose existing FDA-approved therapeutics. One potential strategy targets viral components directly, using existing antivirals and anti-infectives currently used for other diseases. Such efforts include trials of hydroxychloroquine, remdesivir, and ribavirin.^{11,12} Another strategy involves targeting the human proteins, rather than viral proteins, required for SARS-CoV-2 entry and replication.

Study Rationale

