IRB approved flyers that indicate the contact information, including phone numbers, pager numbers, and email of study staff will be posted on the wards and in the emergency department and outpatient clinics.

The PI, one of the sub-investigators, or a study coordinator will be contacted about potential patients. Potential patients will then be approached by study staff about the study to initiate the informed consenting process.

Eligibility Criteria

Inclusion Criteria

1. Male Veterans admitted to a VA hospital.
2. Age \geq 18.
3. Hospitalized on an acute care ward with a diagnosis of COVID-19 contributing to hospitalization.
4. Positive RT-PCR assay for SARS-CoV-2 on a nasopharyngeal swab sample.
5. Severity of COVID-19 illness of level 3, 4 or 5 on the influenza severity scale (see Appendix A) at the time of randomization.
6. The subject (or legally acceptable representative if applicable) must provide written informed consent for the trial.

Exclusion Criteria

2. History of severe hypersensitivity to degarelix or any component of its formulation.
3. History of congenital long QT syndrome or known history of prolonged QT interval OR Fridericia correction formula (QTcF) > 500 msec on electrocardiogram on electrocardiogram performed during screening .
4. Planned discharge within 24 hours of treatment initiation.
5. Subject is planning to conceive or father children within the projected duration of the study, starting with the screening visit through 120 days after the last dose of study treatment.
6. Ongoing usage of a Class IA or Class III antiarrhythmic agent (see Appendix D). At least 5 half-lives must elapse since any prior use of a Class IA or III antiarrhythmic agent prior to administration of study drug.
7. Baseline electrolyte abnormalities of Grade 3 or higher (based on CTCAE v5.0 criteria). Patients may be included if baseline electrolyte abnormalities are corrected to Grade 2 or lower prior to study drug administration.
8. Enrollment in another investigational study within 30 days of Day 1.
9. Myocardial infarction in the past 6 months, severe or unstable angina, or New York Heart Association (NYHA) Class III or IV heart disease.
10. Known psychiatric or substance abuse disorder that would interfere with the requirements of the trial.
11. Child-Pugh Class C liver disease.
12. Use of any of the following hormonal agents:
 - a. Androgen receptor antagonists or agonists within 4 weeks of study enrollment,

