 - Gastrointestinal: Constipation (5%), nausea (1% to 5%), diarrhea

- Genitourinary: Urinary tract infection (5%), erectile dysfunction, testicular atrophy
- Hepatic: Increased serum ALT (10%; grade 3: <1%), increased serum AST (5%; grade 3: <1%)
- Immunologic: Antibody development (antidegarelix: 10%)
- Neuromuscular & skeletal: Back pain (6%), arthralgia (5%), weakness (1% to 5%)
- Miscellaneous: Night sweats (1% to 5%)
- <1%, postmarketing, and/or case reports.
 - Bone metastases (worsening), cerebrovascular accident, depression, hypersensitivity reaction (including anaphylaxis, urticaria, and angioedema), itching at injection site, local soreness/soreness at injection site, malignant lymphoma, mental status changes, myocardial infarction, osteoarthritis, prolonged Q-T interval on ECG, squamous cell carcinoma, unstable angina pectoris.

Dose Modification

No dose modifications will be allowed. Degarelix will be administered as a one-time dose, so dose modification does not apply.

Prohibited Concurrent Treatments and Medications

- Medications listed in the exclusion criteria.
- Any medication that can serve as pro- or anti-androgen, -estrogen, or -progestin (See Appendix B). Dexamethasone was recently reported to reduce COVID-19 severity, so glucorticoids for the purpose of treating COVID-19 are permitted.
- Use of other investigational drugs for COVID-19 treatment within 28 days (or five half-lives whichever is shorter; with a minimum of 14 days from the last dose) preceding the Day 1 of treatment. Use of hydroxychloroquine or chloroquine is permitted.
- Use of hydroxychloroquine and chloroquine are prohibited
- Use of drugs known to prolong QT interval are prohibited

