Subject disposition will be summarized for the ITT population. The number and percentage of patients who completed or discontinued prematurely from the study by the treatment group will be tabulated and tested using Pearson χ^2 test. The number and percentage of patients who discontinued for each reason will be presented for each intervention group. The number and percentage of patients who completed or discontinued prematurely in each intervention group will also be displayed graphically.

Adherence

Patients who change the treatment groups after randomization or have protocol violations will be identified as non-adherence to the treatment. The number and percentage of non-adherence patients will be summarized by the treatment group and tested using Pearson χ^2 test.

Site Effect

Site effect will be evaluated for four participating sites. Balances of the treatment of assignment and the primary and secondary outcomes will be assessed among the four sites. If there is significant associations between the site and treatment assignment and a study outcome at significance level of 0.05 without multiplicity adjustment, the site effect will be adjusted in the corresponding the primary or any secondary outcome along with the other prognostic factors described in the primary and secondary analyses.

Table 3: Summary of Data Analysis Plan

Endpoint Analyses	Statistical Methods	SAS Procedures
Primary Endpoint A composite endpoint of mortality, hospital stay rate, and ECMO or mechanical intubation at 15 days after randomization	Pearson Chi-square tests or Fisher exact tests Logistic regression adjusted for Age, Hypertension, and COPD	1. PROC FREQ PROC LOGISTC

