Following submission to the CDMS, CRF data must pass through a series of quality filters before it is deemed acceptable into the main study database. First, a series of automated logic and range checks will be applied to the data upon data entry and submission and will result in automated requests for confirmation or correction by site personnel. A second series of Quality Checks (QCs) will occur after data submission and will consist of more sophisticated validity checks customized by the clinical data programming staff at the Perry Point CSPCC. These checks may compare values across several different CRFs for consistency; they may trigger requirements for additional forms; or they may calculate necessary values or scores. Reports and listings of data requiring clarifications may also be issued by the data management staff at the Perry Point CSPCC when potential data integrity issues are identified outside of automated means, through a centralized monitoring approach. The Clinical Research Monitors assigned to verify CRF data submissions with source documentation may also issue requests to site personnel for data confirmation, clarification or correction.

If incomplete or inaccurate data or data practices are found, site personnel will be notified and given the opportunity to confirm, correct or clarify the data at the earliest time possible following detection. Only data that have undergone these quality control procedures will be accepted into the study's final database. All confirmations, clarifications and corrections made to CRF data must accord with existing source documentation and must be made in accordance with the ICH guidelines for good clinical practice (GCP). The procedures for confirming, clarifying, or correcting CRF data will be demonstrated at the study's teleconference training meetings and will be detailed within the Data Management Handbook, part of the study's Operations Manual.

All local site investigators (LSI) are responsible for maintaining accurate, legible, complete and up-to-date source documentation and corresponding CRF entries for each patient, including any films, lab reports, ECG tracings, and electronic storage media. All known deviations from the approved study protocol must be documented by site personnel on the protocol deviation CRF and must be acknowledged with a signature from the LSI. Corrections or other changes to the CRFs must be made in line with GCP guidelines using established Perry Point CSPCC procedures.

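### Protocol section 6 both permits and prohibits hydroxychloroquine and chloroquine, and no other text says which rule applies or when

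*Protocol*

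**What the plan says.** The text is in Protocol section 6, under Prohibited Concurrent Treatments and Medications. The third bullet restricts other investigational COVID-19 drugs in a window before Day 1 and closes: "preceding the Day 1 of treatment. Use of hydroxychloroquine or chloroquine is permitted". The fourth bullet is one line: "Use of hydroxychloroquine and chloroquine are prohibited". The fifth adds: "Use of drugs known to prolong QT interval are prohibited".

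Elsewhere the two drugs appear only as background. Section 1 says, of existing antivirals and anti-infectives being repurposed, "Such efforts include trials of hydroxychloroquine, remdesivir, and ribavirin", and a reference title names hydroxychloroquine. The SAP repeats both.

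Two later rules depend on knowing what is allowed. Section 11 (Data Management) requires that "All known deviations from the approved study protocol must be documented by site personnel on the protocol deviation CRF". Section 10 (Adherence) states: "Patients who change the treatment groups after randomization or have protocol violations will be identified as non-adherence to the treatment".

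**The concern.** Adjacent bullets give opposite instructions on the same two drugs. A site investigator whose patient is on hydroxychloroquine, or whose ward team wants to start it, cannot comply with both.

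Three things are at stake. Whether a patient receives a COVID-19 co-treatment could depend on how the site reads the list. The same use could be logged as a deviation at one site and not at another. And the ambiguity stands directly above the ban on QT-prolonging drugs, in a trial where grade 3 to 5 arrhythmia is an event of special interest (section 8). Section 4 also justifies not stratifying by site on the ground that sites will keep supportive care consistent; a contradictory co-medication rule works against that.

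**Working it through.** No arithmetic applies, so the check compares the texts.

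**1. The two sentences side by side.**

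| | Permitting sentence | Prohibiting sentence |
|---|---|---|
| Place | End of third bullet | Whole of fourth bullet |
| Drugs | Hydroxychloroquine, chloroquine | The same two |
| Time period in the sentence | None | None |
| Text just before it | Window before Day 1 for other investigational drugs | The permitting sentence |

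**2. Search for text that decides between them.**
- Eligibility criteria (Synopsis and section 3): neither drug is named. The exclusion for enrollment in another investigational study does not cover ordinary clinical use.
- Best Supportive Care (section 6): off-label treatments are allowed in general; neither drug is named.
- Appendix B (hormonal agents) and Appendix D (antiarrhythmics): neither drug is listed.
- Fifth bullet (QT): no drugs are listed, so it does not settle the matter.
- SAP 3.6 (Concomitant Medications): describes tabulation and possible adjustment, with no rule on use.

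Resolving statements found: 0.

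**3. Readings the text allows.**

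| Reading | Use before Day 1 | Use from Day 1 | On-study use a deviation? |
|---|---|---|---|
| (a) Full ban; permitting sentence is leftover text | Barred | Barred | Yes |
| (b) Exception to the pre-Day 1 window, then an on-study ban | Allowed | Barred | Yes |
| (c) Permitted on study | Allowed | Allowed | No |

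Reading (b) is supported by where the permitting sentence sits and by section 1, which places hydroxychloroquine among drugs in trials. Reading (a) fits a revision that added the fourth and fifth bullets together without deleting the older sentence; the documents cannot confirm this. Reading (c) has some support from the second bullet, which also ends with a permission (glucocorticoids for COVID-19), and that permission does cover on-study treatment. The direct prohibition below counts against (c). The readings disagree about both periods, so the choice changes what a site does.

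**4. How far the effect reaches.** Deviations go on the deviation form (section 11). Patients with violations are counted as non-adherent and compared by arm with a Pearson chi-square test (section 10; SAP 3.4). One document term is deviations and the other is violations, so the link depends on how the sponsor maps the two. Beyond that table the effect stops. The only analysis populations are ITT and Safety, both containing everyone randomised (section 10; SAP 3.3), and SAP 3.6 tabulates actual drug use by arm whichever sentence governs.

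**The case against.** The strongest reply is that this is a drafting slip with an obvious meaning: the permission belongs to the pre-Day 1 bullet and the ban covers the study period. Sites also have ways to reach a common reading: lead investigators monitor and update allowed treatments (section 6), calls with sites are held weekly (section 9), and there is an Operations Manual (section 11), which was not available here. SAP 3.6 provides for adjustment if use of relevant drugs differs between arms.

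Much of this stands, and it is why the point is minor. It does not remove the contradiction. The time split is inferred, leftover wording is equally compatible with the page, and none of the routes described states a rule for these drugs.

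A reader might infer more than the documents support:

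- **A missing stop rule.** One might argue that, even under reading (b), nothing says when earlier use must end. But under (b) the on-study ban is itself the stop time. Asking for an earlier last dose adds a washout the sponsor may have chosen not to require.
- **A lost washout.** The third bullet's "with a minimum of 14 days from the last dose" applies to other investigational drugs. It was never stated as a limit on these two, so no shortfall in days can be computed from it.
- **A contrast with antiarrhythmics.** Section 3 says "At least 5 half-lives must elapse since any prior use of a Class IA or III antiarrhythmic agent prior to administration of study drug". That is an exclusion criterion for a different drug class; its absence here shows no error.
- **A QT hazard.** Neither document says these two drugs prolong QT, and section 6 cites a study finding no QT effect of degarelix by itself. The exclusions for QTcF above 500 msec and for uncorrected Grade 3 or higher electrolyte abnormalities apply under any reading.
- **Bias between arms.** Site investigators and treating staff are blinded, so a site's reading cannot depend on the assigned arm. Differences between sites add noise to the adherence table; they do not systematically favour one arm.

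**Conclusion.** The point holds as an internal inconsistency of minor severity. The contradiction is certain from the text; which rule the sponsor meant is not, and this review takes no position on it. The consequence is inconsistent conduct and deviation recording across sites. Its size in patients cannot be given, because no usage rate is stated. The planned analysis does not change: the overall alpha remains 0.05, the stated power 90%, the sample size 198, and the primary comparison stays on all randomised patients. The conclusion assumes that the Operations Manual contains no overriding rule; if it does, the Protocol should still be brought into line with it.

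**What to change.** Replace the two sentences with one rule of the sponsor's choosing:

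- (a) prohibited throughout: delete the permitting sentence; or
- (b) use before Day 1 does not exclude a patient, but use from Day 1 onward is prohibited: write that time split into the text; or
- (c) permitted on study: delete the prohibition and state how this fits with the bullet on QT-prolonging drugs.

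Notify the sites, so that the same use is recorded the same way everywhere. The cost is a one-sentence amendment and a site notice, with no change to randomisation, sample size or analysis.

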^H Collection of research blood and NP swabs will be attempted at the indicated time points, but it is understood that some of these samples may not be obtained due to logistical reasons, such as safety. Accordingly, the failure to collect the research blood or NP swabs will not be considered a protocol deviation.

^I EKG. EKGs beyond the screening window will be performed per standard of care.

^J Upon discharge, patients will be followed for vital status, need for re-hospitalization, and adverse events.

^K Inflammatory blood tests = CRP, IL-6, ferritin and pro-calcitonin.

Laboratory abnormalities observed during study enrollment will be managed according to local hospital practices and good standard of care. Study teams will focus on electrolyte abnormalities that could impact risk for cardiac events.

Handling of Research Specimens

The research specimens will be transported to UCLA for analysis on the same day of collection whenever possible. If samples cannot be transported to UCLA on the same day of collection, then the samples will be stored within the GLA Medical Center Building 500 Clinical Research Center. In the Clinical Research Center, the NP swabs will be stored at room temperature, and blood specimens will be stored at -20°C.

8. ADVERSE EVENTS AND SERIOUS ADVERSE EVENTS

Overview of Adverse Event Reporting

Timely and complete reporting of safety information assists study management in identifying any untoward medical occurrence. This contributes to patient safety, regulatory compliance and improvements in study design or procedures. In addition, close attention to AEs provides valuable information about the safety and tolerability of study drugs. This study specific safety plan is designed to collect information on the safety and tolerability of the study medications; thus, reporting will be conducted in accordance with the requirements of GCP and other regulatory requirements governing clinical research in the US.

Definitions and recording requirements for this trial are based on the International Conference on Harmonisation Efficacy Guideline 2a: Pharmacovigilance: Clinical Safety Data Management: Definitions and Standards for Expedited Reporting (ICH-E2A), the Code of Federal Regulations (21 CFR 312.32) and CSP Global Standard Operation Procedure (SOP) 3.6.

In HITCH, patients will receive a regimen of FDA approved commercially available degarelix for injection (Firmagon[®]) 240 mg for subcutaneous use or matching placebo. Local Study Investigators, with assistance from their local SC, are responsible for collecting AE and SAE information regarding the patients at their sites.

Non-serious AEs and SAEs will be collected from the time of randomization until 60 days after the last dose of study medication. Throughout the specified duration of AE and SAE collection, data will be collected through spontaneous local SC/LSI/Co-I contact, during in-person study visits, and gathered during telephone contacts and medical record reviews when performed (**see Table of Scheduled Events**). AEs will be collected based on a review of the electronic medical record. If a patient receives care at a non-VA facility for an AE or SAE, study staff should obtain the requisite release of information form(s) from the patient and acquire the pertinent medical records from the facility.

Adverse events that are open will require follow-up reports (if necessary) every 30 days until resolved or until the end of the trial.

Adverse events reported to study staff and deemed related to the study drug(s) and all SAEs will be recorded on an AE or SAE form (respectively) and documented in source records (e.g., the electronic VA medical record and/or the patient's study record). In this way, the site creates a permanent record that provides information on the patient's clinical course while in the study.

Adverse Events (AEs)

An AE is any untoward physical or psychological occurrence in a human participating in research or associated with the use of a drug in a human. An AE can be any unfavorable and unintended event, including an abnormal laboratory finding, symptom, or disease associated with the research or the use of a medical investigational test article. An AE does not necessarily have to have a causal relationship with the research or medical investigational test article. (See 21 CFR 312.32(a) and VHA Handbooks 1058.01 and 1200.05)

Severity of an Adverse Event

Adverse events will be graded according to CTCAE v5.0.

All adverse events that are related to the study intervention or procedures are recorded at each research assessment visit (description, severity, relationship to study intervention, date onset, date resolution).

The following categories are used to convey the severity of an adverse event:

- Grade 1 Mild; – Events require minimal or no treatment and do not interfere with the patient's daily activities.
- Grade 2 Moderate; – Events result in a low level of inconvenience or concern with the therapeutic measures. Interferes with normal daily activities to some extent.
- Grade 3 Severe; – Events interrupt a patient's usual daily activity and may require systemic drug therapy or other treatment. May severely interfere with or prevent normal daily activities
- Grade 4 Life-threatening consequences; – Events requiring urgent intervention
- Grade 5 Death related to AE.

Serious Adverse Event (SAEs)

An AE is considered an SAE if, in the view of either the investigator or sponsor, it results in any of the following outcomes:

- Death;
- A life-threatening AE;

NOTE: The term “life-threatening” in the definition of “serious” refers to an event in which the patient was at risk of death at the time of the event; it does not refer to an event which hypothetically might have caused death if it were more severe.

- Inpatient hospitalization or prolongation of existing hospitalization;
- A persistent, significant, or permanent incapacity or substantial disruption in the patient's body function/structure, physical activities and/or quality of life;
- Congenital anomaly/birth defect; or
- Important medical events that may not be immediately life-threatening, result in death, or require hospitalization may be considered serious when, based upon appropriate medical judgment, they may jeopardize the patient and may require medical or surgical intervention to prevent one of the outcomes listed in this definition. Such events include intensive treatment in an emergency room or at home for allergic bronchospasm; blood dyscrasias or convulsions that do not result in hospitalization; or development of drug dependency or drug abuse. (See 21 CFR 312.32(a) and VHA Handbooks 1058.01 and 1200.05)

A serious problem is a problem in human research or research information security that may reasonably be regarded as:

1. Presenting a genuine risk of substantive harm, to the safety, rights, or welfare of human research subjects, research personnel, or others, including their rights to privacy and confidentiality of identifiable private information; or
2. Substantively compromising a facility's Human Research Protection Program (HRPP) or research information security program.

Relatedness

Relatedness involves an assessment of the degree of causality (attributability) between the study intervention and the event. Site investigators will be asked to provide an assessment of relatedness of the event to the study intervention. The assessment provided by the site investigator is part of the information used by the sponsor (CSP) to determine if the event represents an alteration in the safety profile of the study intervention. All events with a reasonable causal relationship to the study intervention should be considered “related”. A definite relationship does not need to be established. This study will use the following relatedness scale to categorize an event:

- *Definitely Related:* The event is clearly related to the study intervention – i.e. an event that follows a reasonable temporal sequence from administration of the study intervention follows a known or expected response pattern to the suspected intervention that is confirmed by improvement on stopping and reappearance of the event on repeated exposure and that could not be reasonably explained by the known characteristics of the patient's clinical state.

- *Possibly Related*: An event that follows a reasonable temporal sequence from administration of the study intervention follows a known or expected response pattern to the suspected intervention, but that could readily have been produced by a number of other factors.
- *Not Related*: The event is clearly not related to the investigational agent/procedure. - i.e. another cause of the event is most plausible; and/or a clinically plausible temporal sequence is inconsistent with the onset of the event and the study intervention and/or a causal relationship is considered biologically implausible.

Unanticipated Adverse Event:

An AE that is new or greater than previously known, in terms of nature, severity, or frequency of occurrence, or any other unanticipated serious problem associated with the investigation that relates to the rights, safety, or welfare of subjects, as documented in the protocol or other materials approved by the IRB of record or the characteristics of the study population. Such materials may include but are not limited to: the informed consent form, safety plan, clinical investigator's brochure (or CSPCRCC's Drug Information Report), and product labeling (see VHA Handbook 1058.01). The Sponsor (Cooperative Studies Program) will concur or disagree with the site investigator's assessment as to whether an adverse event is anticipated or unanticipated (sometimes referred to as expected/unexpected, respectively).

Expedited Reporting of Serious Adverse Events

All SAEs will be reported by submission of the event into the HITCH reporting system within 3 calendar days of the Study Site Personnel becoming aware of the event. The reporting system will immediately inform the Study Biostatisticians, Clinical Research Pharmacists and Study Chairs. All SAEs found to be attributable or related to the study intervention will be documented as "possibly related" or "related" within the SAE Form.

Expedited Reporting of Adverse Events of Special Interest

Cardiac arrhythmias and thromboembolic events will be considered AEs of special interest. Any cardiac arrhythmia or thromboembolic event of grade 3-5 according to Common Terminology Criteria for Adverse Events version 5.0 (CTCAE v5.0; see Appendix C) will be reported in a manner similar to SAEs, whereby the event will be reported to the HITCH reporting system within 3 calendar days of the Study Site Personnel becoming aware of the event.

Reporting of Related and Unexpected Serious Adverse Events

All SAEs will be assessed by the study Sponsor to determine if an event is anticipated or unanticipated. The source of information that will be utilized in the determination of expectedness will include the HITCH Drug Information Report, the HITCH Informed Consent, published literature, and the FDA Adverse Event Reporting System (AERS). SAEs found by the Sponsor to be both related to the investigational treatment and unexpected will be reported to the VA Chief Research and Development Officer, the FDA, and site investigators after review by the Study Chairs, VA Central IRB, the CSPCRCC Director and the Perry Point CSPCC Director.

Reporting of Adverse and Serious Adverse Events to the DMC

The HITCH Biostatisticians, with coordination from CSPCRPCC, will tabulate and summarize all study intervention related AEs and all SAEs (intervention related or not related) for the DMC on a schedule set by the DMC, but no less than annually. The DMC will also determine when the committee should be unblinded to treatment assignment in reviewing AE/SAE data. The DMC will advise the CSP Director whether the study should continue or be stopped for safety reasons.

Reporting Requirements of the VA Central or Local IRB

Sites are additionally responsible for following the VA Central IRB policy in submitting safety data, unanticipated serious problems, and protocol deviations. The VA Central IRB's most recent policy including a Table of Reporting Requirements, instructions, and forms can be found at <http://www.research.va.gov/vacentralirb/policies.cfm>.

VHA Handbook 1058.01 requires that the VA CIRB must be notified orally and immediately upon becoming aware of any research death that is both unanticipated and related (includes possibly related) to the research. In addition to the oral notification, site personnel must also ensure that a written notification is sent to the VA CIRB within 5 business days of becoming aware of the death (Note: this is different than the 3 calendar day reporting requirement to CSP).

Reporting to the FDA

Any FDA reporting requirements will be handled by the sponsor (CSP), not by individual sites. In addition to prompt reporting to appropriate VA personnel, CSPCRPCC will report SAEs that are both related to study intervention and unexpected to the FDA no later than 15 days from when they are notified. If the SAE is a death or a life-threatening event, this notification will happen within 7 days. In addition, the FDA will be notified (1) for any subject who is withdrawn for safety reasons and (2) for any DMC decision to pause enrollment or terminate the study.

